--	--

	
risk of calcineurin inhibitor-induced hemolytic uremic syndrome/thrombotic thrombocytopenic purpura/thrombotic microangiopathy [HUS/TPP/TMA]).
 
11) Treatment or anticipated treatment with delavirdine (due to potential for loss of virologic response and possible resistance to delavirdine or to the class of non-nucleoside reverse transcriptase inhibitors caused by phenytoin).

Study Design	
This is a phase II single arm, open-label study of SM-88 used with methoxsalen, phenytoin, and sirolimus (MPS) in metastatic HR+/HER2- breast cancer. It is designed to determine efficacy, defined as the objective response rate (ORR) of this investigational treatment in patients with metastatic HR+/HER2-breast cancer. All patients will take SM-88 460 mg PO twice a day and MPS PO once a day. Dose escalation of SM-88 will be permitted. No dose adjustments will be permitted for MPS. Thirty patients will be enrolled in stage 1. If there are 3 or more objective responses among these 30 patients then an additional 20 patients will be enrolled in stage 2; otherwise, the study will be terminated. If there are 8 or more objective responses among the 50 total patients, the null hypothesis will be rejected and SM-88 will be deemed a promising therapy for patients with metastatic HR+/HER2- breast cancer.
  <pre> graph TD subgraph PD [Proposed Design] subgraph S1 [Stage I] S1_N[Metastatic HR+/HER2- N = 30] S1_R1[+ response ≥ 3] S1_T[Study Termination] S1_N -- S1_R1 --> S1_T end subgraph S2 [Stage II] S2_N[Metastatic HR+/HER2- N = 20] S2_R2[+ response ≥ 8 among 50 total patients] S2_F[Further study] S2_N -- S2_R2 --> S2_F end end </pre> 
Figure 1. Study Design

[figure not shown]

Figure 2. Study Schedule

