Patients will be evaluated, including physical exam and laboratory testing, every 4 weeks on Day 1 of each cycle. Laboratory testing will be performed every 2 weeks for the first 2 cycles and then on Day 1 of each subsequent cycle. Restaging will occur every 8 weeks. For patients who achieve a complete response (CR), partial response (PR), or stable disease (SD) confirmed on two consecutive restaging scans by RECIST v1.1 criteria, restaging scans may transition to every 12 weeks. If there is no evidence of progressive disease (PD), as determined by RECIST v1.1, and the patient is tolerating therapy, then the patient will continue with study therapy. Patients will continue to remain on study as long as there is no evidence of PD (according to RECIST v1.1) and the therapy is adequately tolerated.

Two (2) 10.0 mL Streck cell-free DNA collection tubes (DNA BCT catalog #230470) will be collected for cell free DNA (cfDNA) analysis at baseline, C2D1, C3D1, at each additional restaging scan (every 8-12 weeks) and at the time of progression. These vials shall be processed as per the laboratory manual and banked at Georgetown University and stored at -70C.

All findings will be correlated with patient outcomes.

Table 1. Dose Modifications for Toxicities Related to SM-88

Dose Level	SM-88 Dose	Dose Adjustment for Next Treatment
1	460 mg BID (920 mg/day)	Decrease dose to 230 mg BID
-1	230 mg BID (460 mg/day)	Discontinue study treatment for up to 28 days and attempt mitigation; if this dose is not tolerated then patient should be removed from the study

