2.2. Secondary Objectives

To assess:

- Progression free survival (PFS),
- Clinical benefit rate (CBR) at ≥ 24 weeks,
- Duration of response (DOR), and
- Safety/tolerability (adverse events, serious adverse events, incidence of dose delays or dose reductions, treatment discontinuations due to adverse events, and all deaths)

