¹ Cycle length is 4 weeks (+/- 7 days). Evaluations performed at baseline do not need to be repeated on Day 1 of Cycle 1 if performed within prior 28 days, except CBC, biochemical profile, and pregnancy test.

² Biochemical Profile: sodium, potassium, calcium, chloride, bicarbonate, BUN, creatinine, AST, ALT, total bilirubin, albumin, alkaline phosphatase.

³ CBC with differential and biochemical profile must be done within 8 days prior to C1D1, on C1D15 and C2D15 +/- 3 days, and then within 8 days of each subsequent cycle day 1 (C2D1, C3D1, C4D1, etc.).

⁴ Lipid profile must be done at baseline and within 8 days prior to C3D1 and then every 8-12 weeks (at each additional restaging scan) within 8 days of day 1 of that cycle.

⁵ Applies to females of childbearing potential as defined in the eligibility criteria. Serum or urine pregnancy test must be negative within 14 days of C1D1 and within 8 days of each subsequent cycle.

⁶ CT scan of chest, abdomen and pelvis with IV contrast or MRI or PET scan with diagnostic CT (CT can be non-contrast if contraindication to contrast per investigator). Every 8 weeks (+/- 7 days) after start of study therapy. For patients who

achieve a CR, PR, or SD (as demonstrated by RECIST v1.1) confirmed on two consecutive restaging scans, restaging scans may transition to every 12 weeks.

⁷ Brain MRI, preferably with and without IV contrast if history of brain metastases or current suspicious neurologic symptoms. Every 12 weeks (+/- 8 days) after the start of therapy, if patient has a history of brain metastases, whether or not brain metastases have been locally treated.

⁸ SM-88 460 mg PO twice a day D1 – 28; Methoxsalen 10 mg PO daily D1 – 28; Phenytoin 50 mg PO daily D1 – 28; Sirolimus 0.5 mg PO daily D1 – 28.

⁹ Tumor measurements will be conducted according to RECIST v1.1 criteria.

¹⁰ cfDNA will be collected at baseline (pre-treatment), C2D1, C3D1, at each additional restaging scan (every 8-12 weeks) and at progression of disease. Samples will be banked and can be analyzed in the future. If a cycle is delayed then these samples will be collected prior to restarting the study agents. If cfDNA sample has already been collected at the time point and then it is decided that the cycle must be delayed then the cfDNA sample does not need to be re-collected.

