5.1. Dispensation of Study Drug and Treatments Administered

The study drugs are defined as SM-88, methoxsalen, phenytoin, and sirolimus. Patients will self-administer all study drugs by mouth on an outpatient basis. Patients will receive sufficient quantities of each study for 1 cycle of administration on Day 1 of each cycle. Patients will receive bottles of the study drugs from the on-site study coordinator and will be provided with drug diaries (see Appendix C) to record the date and time they took the drugs. On days when patient is scheduled for a clinic visit, the patient should take scheduled SM-88 and MPS doses once all visit assessments have been performed and are within acceptable range, unless otherwise indicated.

It is best to take doses one hour before or two hours after meals, so as to ensure an empty stomach. SM-88 and MPS should be taken together consistently either in the morning or in the evening with a full glass of water. A second dose of SM-88 will be taken 8-16 hours after the SM-88 plus MPS dose -- for example, before bedtime and upon waking up in the morning.

If vomiting occurs, no re-dosing of the patient is allowed prior to the next scheduled dose. If doses of any of the four study drugs are not taken within 4 hours of the intended time, the dose should be skipped and not replaced or made up on a subsequent day. If the AM dose of SM-88 is missed, patients will continue with the PM dose as scheduled. If the PM dose of SM-88 is missed, patients will skip that dose and resume dosing with the AM dose the following day. If a dose of MPS is missed, patients will skip that dose and resume dosing the following day.

Patients should return bottles of the study drugs (empty, partially filled, or full) and their diaries (See Appendix C) to the study site prior to start of next cycle and at the final visit.

Investigational product will be labeled according to applicable regulatory requirements. All investigational products will be stored, inventoried, reconciled, and destroyed according to applicable regulations.

Tyme, Inc. designee ALMAC will provide:

- SM-88 (D,L-alpha-metyrosine) which will be provided in 230 mg capsules. Two 230 mg capsules taken orally twice daily (920 mg daily).
- Methoxsalen will be provided in 10 mg capsules. One 10 mg capsule taken orally once daily.
- Phenytoin will be provided in 50 mg tablets. One 50 mg tablet taken orally once daily.

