5.6. Recommended Dose Modifications

Every effort should be made to administer each investigational product at the planned dose and schedule.

In the event of significant toxicity, dosing may be interrupted, delayed and/or reduced, only as described for each investigational product. In the event of multiple toxicities, treatment/dose modifications should be based on the worst toxicity observed. Patients are to be instructed to notify Investigators at the first occurrence of any adverse symptom.

Treatment/dose modifications may occur independently for each investigational product in the combination based on the observed toxicity and the general guidance, as follows:

- a. SM-88: Dose modifications (dose interruptions, or dose reductions) may be implemented to manage toxicities.
 - i. If SM-88 is held then MPS should be held concurrently.
- b. Methoxsalen, phenytoin, and sirolimus (MPS): No dose reductions are permitted in this study, but if methoxsalen, phenytoin, or sirolimus are considered to be the component associated with a grade 3 or 4 toxicity, the individual components may be discontinued for up to 28 days while mitigating measures are attempted (e.g. changing the timing of phenytoin to address phenytoin related fatigue if experienced). This may be applied to any or all of the MPS components. If after 28 days the grade > 2 toxicity continues, the patient will be removed from the study. If the patient restarts the MPS medication(s) but the toxicity recurs then the 28 day hold clock restarts so that further mitigation efforts can be implemented; if multiple holds are required then it is at investigator discretion if the patient should continue or come off the study.
 - i. If any or all components of MPS are held then SM-88 can be continued at investigator discretion.

The RP2D of SM-88 is 920 mg/day administered as two 230 mg capsules every 12 hours. For patients experiencing a grade 3 or 4 toxicity, dose modifications of SM-88 can be made as outlined in **Table 4 and Table 5**.

Table 4. Dose Modifications for Toxicities Related to SM-88

Dose Level	SM-88 Dose	Dose Adjustment for Next Treatment
1	460 mg BID (920 mg/day)	Decrease dose to 230 mg BID
-1	230 mg BID (460 mg/day)	Discontinue study treatment for up to 28 days and attempt mitigation; if this dose is not tolerated then patient should be removed from the study

Table 5. Management of Toxicities Related to SM-88 and MPS

	SM-88 + MPS
Hematologic Toxicities	

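### The synopsis permits an SM-88 dose escalation that no section defines, and Section 3.4.3 asks for 3 months of contraception where eligibility requires women to use it for at least 6

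*Combined protocol and SAP*

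**What the plan says.** **SM-88 dose.** The Study Design row of the synopsis starts every patient at 460 mg twice daily and then adds: "Dose escalation of SM-88 will be permitted". Table 1, in the same synopsis, gives as the adjustment from that level "Decrease dose to 230 mg BID". Section 5.6 opens with "Every effort should be made to administer each investigational product at the planned dose and schedule" and continues "In the event of significant toxicity, dosing may be interrupted, delayed and/or reduced, only as described for each investigational product". Its item a reads "SM-88: Dose modifications (dose interruptions, or dose reductions) may be implemented to manage toxicities". Footnote 8 of the study calendar has "SM-88 460 mg PO twice a day D1" to 28, and Section 5.1 dispenses the same 920 mg per day. The safety objective in Section 2.2 counts "incidence of dose delays or dose reductions, treatment discontinuations due to adverse events, and all deaths"; it does not count escalations.

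**Contraception.** Section 3.4.3 asks for birth control from consent until 3 months after the final dose of SM-88 or MPS. It adds a separate 6-month rule for men on conception and sperm donation. Inclusion criterion 13 and the Appendix A checklist set a minimum of 6 months after last treatment for women of childbearing potential.

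**Recovery after a hold.** Section 6.8.1 requires recovery within 28 days to Grade 1, or to baseline if the patient entered at Grade 2; otherwise treatment stops for good. Table 5 sets numerical limits for hematologic events and a Grade 1 or baseline rule for non-hematologic ones. Section 5.6 item b covers holds of individual MPS components and removes a patient only if a toxicity above Grade 2 persists after 28 days.

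**The concern.** The synopsis gives investigators permission to raise the dose of an investigational drug without saying how far, when or in whom. The restrictive clause in Section 5.6 applies in the event of significant toxicity. The body therefore does not expressly forbid an increase in a patient who tolerates treatment well, and no precedence rule cancels the synopsis. If the permission were used, the response rate would no longer describe the 460 mg BID regimen alone.

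For contraception, Section 3.4.3 is the section headed for birth control and is where a site would naturally look when counselling. Premenopausal women are eligible (inclusion criterion 6), and Section 6.8.3.1 warns that phenytoin may harm a fetus. Counselling from 3.4.3 alone would fall short of what the patient agreed to at entry.

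The recovery wording matters less. A site managing a cytopenia should not have to work out which of two limits applies.

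**Working it through.** The point rests on comparing sections. The only arithmetic is counting and subtraction.

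**(a) Dose levels**
- Tables 1 and 4 list level 1 = 460 mg BID and level -1 = 230 mg BID, which is 2 levels.
- Levels above 460 mg BID: 0.
- Escalation triggers, timings or ceilings in the synopsis, 5.1, 5.6, Tables 1, 4 and 5, or calendar footnote 8: none.
- Scale, as an illustration only: one extra 230 mg capsule per dose would give 3 × 230 × 2 = 1,380 mg/day. Section 1.3 reports 230 to 960 mg/day for the 77 patients treated with SM-88 plus MPS. No document proposes the higher dose; the figure shows only that an unbounded permission can leave the range of experience summarised there.

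**(b) Contraception after the last dose**
- Section 3.4.3, general rule: 3 months.
- Section 3.4.3, men (conception, sperm donation): 6 months.
- Inclusion criterion 13, women of childbearing potential: at least 6 months.
- Appendix A, same women: at least 6 months.
- Shortfall for women: 6 − 3 = at least 3 months. Six months satisfies every statement; three months does not.

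**(c) Recovery within 28 days**
- Hematologic, Table 5: resume at hemoglobin ≥ 8 g/dL, ANC ≥ 1,000/mm³ or platelets ≥ 50,000/mL. By the table's own cut-offs these values mean only that the event is no longer Grade 3.
- Hematologic, Section 6.8.1: Grade 1, or baseline if Grade 2 at entry. A patient who was not Grade 2 at entry and whose count has only just left Grade 3 by day 28 resumes under Table 5 and stops under 6.8.1.
- Non-hematologic, Table 5: Grade 1 or baseline within 28 days. This is essentially the 6.8.1 rule, so there is no material difference here.

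**Background check on the design.** With stage 1 stopping at 2 or fewer responses in 30 and rejection at 8 or more in 50, the probability of rejection is the sum over x = 3 to 30 of P(X₁ = x) × P(X₂ ≥ max(0, 8 − x)), where X₁ is Bin(30, p) and X₂ is Bin(20, p). It is 0.0955 at p = 0.095 and 0.802 at p = 0.20, in line with the stated 0.1 and 0.8. None of the wording above enters this calculation.

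**The case against.** The strongest reply on dose is that this is one wrong word. The preceding sentence fixes 460 mg BID, Table 1 in the same synopsis shows only a decrease, and every operational section agrees. That stands, and it makes the practical risk small. It does not remove the permission from the current text. Another possible reading is a return from 230 to 460 mg BID after recovery. No section sets a rule for that either, so it would also need writing down.

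On contraception, the stricter rule binds at eligibility and a site that follows 6 months meets both. That also stands. The weak spot is a site that reads only 3.4.3. The consent form is not among these documents, so what patients are actually told cannot be checked.

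A reader might infer that the protocol holds three conflicting recovery rules. The documents do not support that. Table 5 and 6.8.1 essentially agree on non-hematologic events. For hematologic events, 6.8.1 describes itself as general and sends the reader to Table 5 for specifics, so the ordinary reading is that Table 5 governs. Section 5.6 item b deals with holding a single MPS component, during which SM-88 may continue, and Section 5.6 allows each product to be modified independently. A different threshold there may be deliberate.

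**Conclusion.** Parts (a) and (b) are wrong as written and should be fixed: an escalation permission with 0 defined levels above 460 mg BID, and a contraception period at least 3 months shorter than eligibility requires for women. Part (c) is an optional clarification confined to hematologic toxicity.

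The conclusion assumes that no escalation above 460 mg BID was intended, which the rest of the dosing text supports but which the sponsor should confirm. A reader might also infer that patients were given higher doses, that harm followed, or that the trial's error rates are affected. Nothing in the documents shows the first two. The third does not follow, because the decision rule and sample size do not depend on these sentences.

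**What to change.** 1. **Synopsis, Study Design.** Replace the escalation sentence with one stating that SM-88 may be reduced as set out in Section 5.6 (Tables 4 and 5) and that escalation above 460 mg BID is not permitted. If a return from 230 to 460 mg BID was meant, define it in Section 5.6.
2. **Section 3.4.3.** Change 3 months to at least 6 months after the last dose, and check that the consent form gives the same period.
3. **Section 6.8.1, optional.** After the reference to Table 5, add that the Table 5 recovery limits govern for hematologic toxicities.

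Leave the Grade > 2 threshold in Section 5.6 item b as it is. Substituting the Table 5 level would newly remove patients whose MPS-attributed non-hematologic toxicity settles at Grade 2. Under Sections 3.6.2.1 and 4.3.12.2, patients who stop for intolerance before first restaging without progression are non-evaluable and replaced, so that edit could change who counts for the primary endpoint.

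The cost is one sentence each for items 1 and 2, one clarifying sentence for item 3, and a consent-form check. Sample size, endpoints and analyses do not change.

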Multi-Institutional Trial Coordination	
Personnel
 
At each site, personnel dedicated to this protocol will be:
 
 - A study PI - A research coordinator - A data manager 
In addition, the clinical research organization (CRO), KPS will oversee the multi-institutional coordination.
 
Patient Enrollment
 
If a patient is being screened for enrollment, the local research coordinator must send an email within 24 hours containing the patient's name to the local principal Investigator (PI), and to the CRO. If a patient is successfully screened, the local research coordinator must send all supporting documentation to the Principal Investigator. Patients should not start therapy until the Principal Investigator or the local PI and the CRO have reviewed the patient's records and confirmed that the patient is indeed eligible for enrollment.
 
Data Collection and Management
 
Patient data will be entered into the on-line accessible database. This database is housed at Lombardi-Georgetown, but is accessible anywhere there is internet access. The data manager and research coordinator at each site will attend an on-line training session so that they may learn how to enroll data into the data base. All screening data should be entered prior to starting therapy, and all ongoing patient data should be entered within 10 business days of each patient visit.
 
Conference Calls
 
The Principal Investigator and the Co-Investigators will review the data including safety monitoring at frequent disease group meetings and network disease group

	
teleconferences. The Investigators shall regularly review toxicities and follow up on results of patients enrolled on the study.
 
Trial Auditing
 
The company will arrange all primary source documents for the patients to be audited by a Tyme-appointed CRA. This will include collecting copies of the primary source data for any patients treated at other sites.

Duration of therapy	All drugs will be administered until disease progression or unacceptable toxicity is observed.

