
causality, toxicity grading, and action taken with regard to trial treatment. The percentage of patients experiencing an adverse event at a given severity, NCI CTCAE toxicity grade, and relationship to study drug will be provided. The number of patient deaths throughout the study will be summarized.

Descriptive statistics of genomic changes will be used to characterize cell-free DNA (cfDNA) analysis during the therapy as well as scheduled collection time points.

P-values less than 0.05 will be considered significant. All statistical analyses will be performed using RStudio (Version 0.99.902) and SAS (Version 9.4).

Number of Centers

In order to recruit 50 patients with advanced HR+/HER2- breast cancer in a timely manner it will be critical to have access to a large pool of potential patients. Thus, we propose a multicenter trial. Georgetown-Lombardi will act as the primary site, and a dedicated CRO will oversee patient enrollment and on study activities at other sites. Georgetown-Lombardi will also be responsible for generation of the case report forms, which can be accessed through an on-line data entry portal (training for this portal can be done on-line).

1. Background and Justification

In 2019, there were approximately 270,000 new breast cancer diagnoses and 42,000 breast cancer-related deaths in the United States (Siegel, Miller et al. 2019). Hormone receptor-positive (HR+) breast cancer accounts for approximately 70% of breast cancers. First-line systemic therapies for advanced or metastatic HR+ breast cancer are typically endocrine therapy alone or endocrine therapy plus a cyclin dependent kinase 4/6 inhibitor (CDK4/6i) and the next line of therapy is typically fulvestrant, an intramuscular selective estrogen receptor degrader (SERD) +/- a CDK4/6i depending on whether the patient received a CDK4/6i as first-line. Although many metastatic HR+/HER2- breast tumors initially respond to these therapies, most eventually become resistant leading to progressive disease and the need for intravenous (IV) chemotherapy or toxic targeted therapies such as the mammalian target of rapamycin (mTOR) inhibitor, everolimus, plus exemestane. There is a critical unmet need for oral and less toxic therapies for this very common disease.

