3.6.2. Evaluable Patients

3.6.2.1. Objective Response Evaluable

To be considered evaluable for the primary endpoint of ORR as determined by RECIST v1.1, the patient must meet all inclusion/exclusion criteria and remain on study treatment at least until the first re-staging after cycle 2 of SM-88 used with MPS unless they are taken off for disease progression, clinical progression, or death related to the underlying solid tumor malignancy (as determined by the treating oncologist) in which case they **will be** deemed evaluable. However, patients who have initiated therapy and who withdraw from the study for any reason other than clinical or radiographic progression, or death believed unrelated to their underlying solid tumor malignancy **will not be** considered evaluable for response. Reasons for patients who have initiated therapy, but are no longer evaluable for response could include (but are not limited to):

- The patient cannot tolerate therapy despite dose modifications, and there is no evidence of clinical/radiographic disease progression at the time of stopping therapy
- An unexpected and/or unrelated medical illness, such as a stroke or myocardial infarction that is considered unrelated to the underlying solid tumor malignancy
- An unexpected trauma or death that is considered unrelated to the underlying solid tumor malignancy

If a patient is deemed to be non-evaluable for the primary endpoint of ORR they will be replaced.

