3.7.2. Patient Enrollment

Enrollment at the sites will be competitive. If a patient is being screened for enrollment, the local research coordinator must send an email containing the patient's initials to the local PI, to [name], and to the Georgetown University's Multicenter Project Management Office. If a patient is successfully screened, the local research coordinator must send all supporting documentation to Georgetown University's Project Management Office by secure email to confirm eligibility. Patients should not start therapy until [name] and Georgetown University's Project Management Office have reviewed the patient's records and confirmed that the patient is indeed eligible for enrollment.

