4	Completely disabled. Cannot carry on any self-care. Totally confined to bed or chair.

APPENDIX B: PATIENT REGISTRATION FORM**A Phase II trial of SM-88 in patients with metastatic hormone receptor-positive and HER2-negative (HR+/HER2-) breast cancer**

Study ID (IRB#): _____ Patient Initials: _____

Instructions: This form and all supporting documentation should be completed by the research staff and scanned/mailed to the Georgetown Project Managers ([REDACTED]) and Study PI ([REDACTED]).

Patient may not start treatment until eligibility is verified and Patient Study ID is assigned by Georgetown PMs.

Enrolling Site:

- MedStar Georgetown University Hospital (Lombardi Comprehensive Cancer Center)
- MedStar Washington Hospital Center
- MedStar Franklin Square Medical Center
- MedStar Good Samaritan Hospital
- Hackensack University Medical Center

1. Site PI: _____
2. Enrolling MD: _____
3. Date Informed Consent signed: ____ / ____ / ____
4. Date HIPAA Authorization signed: ____ / ____ / ____
5. Proposed Start Date for Treatment: ____ / ____ / ____
6. Treatment Location: _____
7. Date of Last Systemic anti-cancer therapy: ____ / ____ / ____
8. Prior Therapies (Date Initiated/Type):

9. Please fax documentation supporting eligibility per protocol (check those included):

- Eligibility Checklist
- Pathology Report
- Physicians Note
- Baseline CT/RECIST
- Laboratory Results (per protocol)
- Past Medical History
- ECOG score
- Other _____

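### The synopsis and the body of the protocol set different eligibility releases before first dose; separately, the ORR rules disagree on whether a dosed patient later found ineligible is counted or replaced

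*Combined protocol and SAP*

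**What the plan says.** **Release before first dose.** The synopsis (Multi-Institutional Trial Coordination, Patient Enrollment) bars the start of therapy "until the Principal Investigator or the local PI and the CRO have reviewed" the patient's records and confirmed eligibility. The coordinator "must send all supporting documentation to the Principal Investigator", but that person's review is not made mandatory. Under Number of Centers the synopsis adds that "a dedicated CRO will oversee patient enrollment and on study activities at other sites".

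Section 3.7.2 reads: "Patients should not start therapy until [name] and Georgetown"'s Project Management Office have done the review. It gives the CRO no role and offers no local-PI alternative. Appendix B (the registration form) reads: "Patient may not start treatment until eligibility is verified and Patient Study ID is assigned by Georgetown PMs".

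**Eligibility and the response count.** For ORR evaluability, 3.6.2.1 requires that "the patient must meet all inclusion/exclusion criteria and remain on study treatment at least until the first re-staging after cycle 2", with exceptions for progression and tumour-related death. It then states: "If a patient is deemed to be non-evaluable for the primary endpoint of ORR they will be replaced". Section 4.3.12.2 repeats the eligibility condition and the replacement rule, though it names cycle 3 rather than cycle 2 for the re-staging. Section 8.4.1 and the synopsis statistical section compute ORR in everyone who had at least one cycle. Section 7.1.1 defines response-evaluable patients without an eligibility condition.

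**The concern.** The pre-dose check enforces the exclusions tied to the study drugs, such as phenytoin hypersensitivity, photosensitivity disease and calcineurin inhibitors. With two release rules in the current text and no order of precedence, a site can comply with the synopsis and breach 3.7.2. Where the two differ, the enrolling site's own PI stands in for the lead investigator, and a CRO stands in for the Georgetown office.

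The second matter sits beside the first and does not depend on it. Response is assessed by the investigator in an open-label trial (7.3, 8.2). If eligibility can be re-judged after the scans are read, and an ineligible patient is then replaced, the judgement can be influenced by the outcome. What is at stake is the ORR estimate and the two decision counts, 3 of 30 and 8 of 50.

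**Working it through.** **1. The release texts side by side**

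| Item | Synopsis | Body and appendices |
|---|---|---|
| Who must clear the patient | PI or local PI, and CRO | Lead investigator and Georgetown office (3.7.2); Georgetown project managers verify and assign ID (Appendix B) |
| Multicentre oversight | CRO | Georgetown office (3.7.1) |
| Screening email | Patient's name, to local PI and CRO | Patient's initials, to local PI, lead investigator and Georgetown office (3.7.2) |
| Source-document audit | CRA appointed by the drug supplier | Arranged by Georgetown office (3.7.5) |

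The synopsis phrase can be read as (PI) or (local PI and CRO), or as (PI or local PI) and (CRO). On both readings, local PI plus CRO is sufficient. The lead-investigator requirement comes from 3.7.2; Appendix B makes the project managers the check and sends the form to the study PI as well.

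**2. The counting rules for a dosed patient found ineligible later**

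- 3.6.1 treats ineligibility as screen failure only before therapy starts, so it does not apply.
- 3.6.2.1 and 4.3.12.2: not evaluable, replaced, with no time limit on the judgement.
- 8.4.1 and the synopsis statistical section: counted after one cycle.
- 7.1.1: no eligibility condition.

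The same patient is replaced under one pair of sections and counted under the others.

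**3. The stated design reproduced**

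Inputs from 8.3: p0 = 0.095, p1 = 0.20, stop at 2 or fewer of 30, reject at 8 or more of 50, type I error 0.1, power 0.8.

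P(reject) = Σ over x ≥ 3 of P(X1 = x) · P(X2 ≥ 8 − x), with X1 ~ Bin(30, p) and X2 ~ Bin(20, p).

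At p = 0.095:

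- x = 3: 0.2351 × 0.0357 = 0.0084
- x = 4: 0.1666 × 0.1156 = 0.0192
- x = 5: 0.0909 × 0.2947 = 0.0268
- x = 6: 0.0398 × 0.5790 = 0.0230
- x = 7: 0.0143 × 0.8642 = 0.0124
- x ≥ 8: 0.0057

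The sum is 0.0955. The same formula at p = 0.20 gives power 0.802. Both agree with 8.3, taking 0.1 as a ceiling.

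**4. Illustration of selective replacement**

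The documents give no number of ineligible dosed patients, so k = 1 to 3 is an assumption. In both models below only non-responders are removed.

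- Model A: k non-responders are replaced, approximated by adding k patients to one stage (30 + k in stage 1, or 20 + k in stage 2) with unchanged cut-offs.
- Model B: k patients are ineligible, and each is replaced only if not responding. Those k places then respond with probability 1 − (1 − 0.095)² = 0.181.

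| k | A: stage 1 / stage 2 | B: stage 1 / stage 2 |
|---|---|---|
| 1 | 0.1047 / 0.1039 | 0.1034 / 0.1028 |
| 2 | 0.1143 / 0.1125 | 0.1117 / 0.1103 |
| 3 | 0.1243 / 0.1214 | 0.1203 / 0.1181 |

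If removal is unrelated to response, each replacement has the same response probability as the patient removed. The error then stays at 0.0955 and the power at 0.802.

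**The case against.** A reader might infer that the synopsis lets a site release its own patient unchecked. It does not. The CRO is outside the site and must review, and the documents go to the Principal Investigator. Appendix B lists all five sites and bars treatment until the Georgetown project managers have acted; Appendix A is completed before registration and provides for emailing it to the same office. At the lead site the local PI may be the lead investigator, so the gap mainly concerns the other sites. The CRO's release role appears only in the synopsis, which suggests text that was not updated. All of this stands. It limits the practical risk but does not settle which rule governs.

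A reader might also infer that the mismatch inflates the type I error. The documents do not support that. The eligibility condition in 3.6.2.1 and 4.3.12.2 applies under either release rule, since a centrally cleared patient can also be found ineligible later. Correcting the synopsis alone would leave the calculation unchanged, and nothing shows how many more ineligible patients the synopsis wording would let through.

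Nor is it settled that such a patient would be dropped from the response count, because 7.1.1, 8.4.1 and the synopsis statistics point the other way. The examples of non-evaluability in 3.6.2.1 and 4.3.12.2 are intolerance, unrelated illness, and unrelated trauma or death. No section describes an eligibility ruling after a scan. However, those lists are expressly not exhaustive, and the eligibility condition is explicit, so removal after the outcome is possible under the text.

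**Conclusion.** There are two inconsistencies in the current text, and they should be kept apart.

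First, the pre-dose release rule differs between the synopsis and 3.7.2 with Appendix B, with no precedence stated. A site could dose a patient without the central check; that it would do so is not shown, and Appendix B should normally prevent it. This part has no calculable size.

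Second, whichever release rule applies, the plan does not say consistently whether a dosed patient later found ineligible belongs in the ORR count. The design has little slack below 0.10. With perfect selection of non-responders, one replaced patient takes the type I error to about 0.103–0.105, and three take it to 0.118–0.124. These figures are a worst case and rest on an assumed number of patients. They do not predict what will happen in this trial.

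**What to change.** 1. Replace the synopsis text on Personnel, Patient Enrollment and Trial Auditing, and the CRO sentence under Number of Centers, with the wording of 3.7.1, 3.7.2 and 3.7.5. One central check then binds every site, and the patient's name no longer goes into the screening email. The cost is wording; sites already owe this check under 3.7.2 and Appendix B.

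2. Reconcile 3.6.2.1, 4.3.12.2, 7.1.1, 8.4.1 and the synopsis statistical section on a single ORR population. The simplest rule is that eligibility for the ORR count is the decision recorded at release before first dose, so that a released and dosed patient is neither removed nor replaced for ineligibility found after response is known. Editing only 3.6.2.1 and 4.3.12.2 would leave the other definitions in conflict.

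The second change costs more than wording, because it settles the primary analysis set. Dosed patients later found ineligible would stay in the denominator, which may lower the ORR slightly.
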